# 9.5.2 Romidepsin Dose Modification in Case of Cardiac Toxicity

The guidelines for cardiac monitoring and timing of ECG assessments are presented in Table 5. Prolongation of  $QTc/QTf \ge 500$  msec is considered to be an alert associated with romidepsin administration.

Table 5: Dose alteration based on cardiac abnormalities					
Parameter/Symptoms	Change	Action	Dosing/ Continuation		
Sinus tachycardia	Pulse >140/min after recumbency	Hold further dosing and treat appropriately. If	If resolved, restart romidepsin at reduced dose as per table 3. If not resolved, take off study.		
Atrial dysrhythmia (SVT, atrial fibrillation, or atrial flutter)	New occurrence	desired, a local cardiologist may be consulted.			
Prolongation of QTc/QTf compared to baseline	To ≥500 msec				
Heart rate	> 120 bpm with > 20 bpm increase from previous evaluation;				
Ventricular tachycardia	≥3 beats in a row				
Ventricular fibrillation; Torsade de Pointes	New occurrence	Hold further dosing and treat appropriately. The MSK PI should be notified immediately and local cardiologist should be consulted.	Hold further dosing until MSK PI and cardiologist evaluation is complete		
A subsequent episode above, despite dose red	_	Take off study			
T-wave morphology	Inversion of ≥4 mm a	Hold further dosing and treat appropriately. If desired, a local cardiologist may be consulted.	If resolved, restart romidepsin at reduced dose of 10 mg/m² In some patients, ST segment and T-wave morphology changes may recur despite a dose reduction to 10mg/m². In such cases, further treatment should be held until the ECG changes resolve. If the patient experiences no concomitant clinical events, treatment may be resumed at the reduced dose of 10 mg/m² If not resolved, take off study		
ST-segment	Depression of ≥2 mm b				

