#### 9.3.2 Dose Escalation

Subjects enrolled into the phase 1b portion will enroll at dosing level 1 with three patients per dosing level (3+3 design). A cycle will be 21-days. Based on toxicity

and activity seen during the phase lb portion, additional dose levels and/or alternate 28 day cycle may be explored through an amendment. The carfilzomib will be given intravenously weekly on days 1 and 8. The romidepsin will be given intravenously on days 1 and 8. The lenalidomide will be given as a once a day oral drug given on days 1-14. It is preferred that romidepsin be administered prior to carfilzomib.

TABLE 1: Phase I Dose Escalation			
Dose	Romidepsin	Lenalidomide	Carfilzomib
Level			(mg/m²)
-1	8 mg/m 	10 mg	20
1	8 mg/m 	15 mg	36
2	8 mg/m 	15 mg	45
3	10 mg/m 	20 mg	45
4	10 mg/m 	20mg	56
		J	

If all three patients complete one cycle of therapy without a DLT at the respective

- dose level then the subsequent dose level can be accrued.

  A DLT is defined in cycle 1 of the phase I portion as:

   Non-hematologic toxicity of grade ≥3 (attributed to study drugs with the exception of alopecia, nausea, or grade ≥3 vomiting not responsive to antiemetics)
  - Hematologic grade 4 toxicity (attributed to study drugs) defined as grade 4 thrombocytopenia of any duration; grade 4 neutropenia lasting more than 5 days; or grade 4 anemia unexplained by the underlying disease
  - Grade ≥3 thrombocytopenia with clinically significant bleeding
  - Febrile neutropenia of any duration (ANC <1.0K/ µL with fever 38.5°C)
  - Inability to receive day 1 of cycle 2 due to continued drug-related toxicity including Grade ≥ 2 toxicity that does not resolve to Grade ≤ 1 by the start of the next cycle.
  - Grade 3 thrombocytopenia or neutropenia (attributed to study drug) within cycle 1 that results in a) ≥ 4 day delay in any romidepsin or carfilzomib dose or b) missing greater than 4 days of lenalidomide. (This criteria only applies to the **phase lb portion** and does not apply to the phase Ila stopping rules).

After the MTD is determined by either DLT or accrual of six patients without DLT at dose level 4 in the first cycle accrual to the phase Ib portion will be considered closed. The MTD from the phase lb study will be used for the phase lla portion.

Of note, only patients who complete ≥80% of the doses of carfilzomib, romidepsin and lenalidomide during the first cycle will be evaluable for MTD. Patients who do

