#### Treatment Plan: carfilzomib/romidepsin/lenalidomide Phase Ila

The phase IIa portion is planned to include 20 patients. Each disease cohort, B-and T-cell lymphoma, will have 10 patients. Patients treated at MTD in the phase Ib cohort (if measurable disease at enrollment) will be included towards the 20 patient total in the phase IIa. The MTD has been determined to be dose level 1; 8 mg/m² romidepsin on days 1 and 8, 15 mg lenalidomide from days 1 - 14, and 36 mg/m² carfilzomib on days 1 and 8. The phase IIa cohort will be evaluated both collectively and by disease subtype.

Patients that have received long-term therapy (greater than one year) with response will be allowed to have their schedule modified to allow less frequent dosing per investigator and primary investigator discretion.

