# 9.5.2 Instructions for Dose Modifications or Interruption During Phase 1 Cycle 2 and beyond and phase 2 all cycles

Dose delay and dose reduction rulesare as follows and in the table below. The following dose modification criteria are applicable to adverse events related to study drugs:

- In the event of dose reduction due to toxicity all agents will be reduced as per Table 2, 3, 4. If an agent is already at its lowest dose per tables 2,3,4 then the other agents will be reduced. If the lowest doses are not tolerated the subject will be removed from the study.
- For treatment interruptions during a cycle, the 21-day schedule of each cycle will continue to be followed. Missed doses of lenalidomide, carfilzomib and romidepsin are not made up. For treatment interruptions that delay the scheduled start of a new cycle, when toxicity has resolved as required to allow the start of a new cycle, the restart day of therapy becomes Day 1 of the next cycle.
- If a patient is at the lowest dose level and deriving benefit from therapy, they may continue on protocol therapy despite ≥ grade 3 hematologic toxicity or non-clinically significant non-hematologic toxicity after discussion with the MSK principal investigator. A delay of planned study therapy of greater than 21 days with result in removal from study.

TABLE 2: Lenalidomide Dose Modification Steps		
Current Lenalidomide Dose	One Level Dose Reduction	
20 mg daily on Days 1-14 every 21 days	15 mg daily on Days 1-14 every 21 days	
15 mg daily on Days 1-14 every 21 days	10 mg daily on Days 1-14 every 21 days	
10 mg daily on Days 1-14 every 21 days	5 mg daily on Days 1-14 every 21 days	

TABLE 3: Romidepsin Dose Modification Steps		
Current Romidepsin Dose	One Level Dose Reduction	
10 mg/m  daily on Days 1,8	8 mg/m² daily on Days 1,8	
8 mg/m² daily on Days 1,8	5 mg/m² daily on Days 1,8	
5 mg/m² daily on Days 1,8	5 mg/m² daily on Days 1	
Carfilzomib Dose Modification Steps		
Current Carfilzomib Dose	One Level Dose Reduction	
56 mg/m 	45 mg/m 	
45 mg/m 	36 mg/m 	
36mg/m 	20 mg/m 	

TABLE 4: Dose Modifications for Lenalidomide, Carfilzomib and Romidepsin for Phase 1 cycle 2 and beyond/ Phase 2 all cycles		
NCI CTC Toxicity Grade	Dose Modification Instructions	
, , ,	(also see Instructions for Initiation of a New Cycle above)	

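### Table 5 restarts romidepsin at 10 mg/m² after ST or T-wave changes and calls this a reduction, but the MTD is 8 mg/m²

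*Combined protocol and SAP*

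**What the plan says.** The protocol contains two sections numbered 9.5.2. The one on cardiac toxicity holds Table 5. Its T-wave and ST-segment rows tell sites to hold dosing and treat, and then: "If resolved, restart romidepsin at reduced dose of 10 mg/m²". The same cell covers changes that recur at that dose: once the ECG has resolved, and if there was no concomitant clinical event, "treatment may be resumed at the reduced dose of 10 mg/m²". In all, the cell gives 10 mg/m² three times as the reduced dose.

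The rows above it in Table 5 (sinus tachycardia, atrial dysrhythmia, QTc/QTf prolongation, heart rate, ventricular tachycardia) use a different rule: "If resolved, restart romidepsin at reduced dose as per table 3".

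On the dose that patients actually receive, the phase IIa treatment plan states: "The MTD has been determined to be dose level 1; 8 mg/m² romidepsin on days 1 and 8". Section 9.3.2 adds: "The MTD from the phase lb study will be used for the phase lla portion".

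Table 3, in the other Section 9.5.2, gives the step down from 8 mg/m² as "5 mg/m² daily on Days 1,8".

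**The concern.** A dose reduction has to end below the dose that the patient was on. Table 5 names a fixed dose, with no reference to the current one, and that dose is above the one given to every patient who starts at the MTD. A site that follows the row would raise romidepsin directly after an ECG change that the protocol treats as serious. Section 10.5 lists both findings as cardiac alerts, and ST depression of ≥2 mm at screening is an exclusion criterion in Section 6.3.

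The first issue is patient safety. The second is interpretation: phase IIa exists to characterise toxicity at the MTD, and cycles given above it would not describe that dose.

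**Working it through.** The plan has no statistical figure to reproduce here. The check is whether 10 mg/m² can be reached as a reduced dose from any dose in the protocol.

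**Inputs**

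- Table 1 (Section 9.3.2), romidepsin by dose level: level -1, 8; level 1, 8; level 2, 8; level 3, 10; level 4, 10 mg/m².
- MTD and phase IIa dose (phase IIa treatment plan): level 1, 8 mg/m² on days 1 and 8.
- Table 3 steps: 10 to 8 mg/m²; 8 to 5 mg/m²; 5 mg/m² on days 1 and 8 to 5 mg/m² on day 1 only.
- Table 5, ST and T-wave rows: restart at 10 mg/m².

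**Step 1: can 10 mg/m² be the result of a reduction?** Every Table 3 step ends at 8 or 5 mg/m², and none ends at 10. A reduction to 10 needs a starting dose above 10, and the highest dose in Table 1 is 10. It is therefore a reduction at 0 of 5 levels.

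**Step 2: size of the change.** Relative change = new dose / current dose − 1.

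| Current romidepsin | Table 5, ST/T-wave rows | Table 3 |
|---|---|---|
| 8 mg/m² (MTD; levels -1, 1, 2) | 10/8 − 1 = +25% | 5/8 − 1 = −37.5% |
| 10 mg/m² (levels 3, 4) | 10/10 − 1 = 0% | 8/10 − 1 = −20% |
| 5 mg/m², days 1 and 8 (reduced once from 8) | 10/5 − 1 = +100% | day 1 only: 5/10 per cycle − 1 = −50% |

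In the last cell the per-cycle total falls from 5 + 5 = 10 to 5 mg/m².

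**Step 3: consistency within Table 5.** Take two patients on 8 mg/m². One has QTc/QTf ≥500 msec that resolves and restarts by Table 3 at 5 mg/m². The other has ST depression of ≥2 mm that resolves and restarts at 10 mg/m². The second receives 10/5 = 2 times the dose of the first, after a finding in the same list of alerts.

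**Step 4: recurrence.** The ST and T-wave cell allows dosing to resume again at 10 mg/m² after a further episode. Exposure above the MTD could therefore continue over later cycles.

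**Step 5: what is not affected.** The escalation and stopping probabilities in Section 14.0 do not use the restart dose and do not change.

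**The case against.** Four points can be made for the protocol.

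- **The investigator decides.** Section 10.5 leaves delay, dose reduction or withdrawal after an alert to the investigator, with a cardiologist if preferred, and describes the Table 5 reductions as recommended. This makes the row less binding and harm less likely. But the same section sends the investigator to Table 5 for the dose, as does footnote 2 of the study calendar (Appendix G), so the number that guides the decision is still the wrong one.
- **The right step is given elsewhere.** The general rule in Section 9.5.2 reduces all agents by Tables 2, 3 and 4, which gives 5 mg/m² from 8. Table 4 also requires one level lower for related grade ≥3 toxicity and names myocardial ischemia. However, the general rule does not say that it overrides Table 5, which is the specific instruction for these findings. The Table 4 row needs grade 3, whereas Table 5 is triggered by the ECG measurement alone.
- **The error is plain to a reader.** The word *reduced* shows the intent, and a careful site would query an increase. That is probably true in most cases, but a safety table in a multicenter trial should not rely on sites overruling its number.
- **10 mg/m² has been tolerated.** Section 3.5 reports romidepsin 10 mg/m² with lenalidomide 25 mg. That was a doublet without carfilzomib, and the report does not concern re-treatment after ECG changes.

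It also stands that the consequences are conditional. They need a qualifying ECG change, its resolution, and re-dosing at 10 mg/m². The documents give neither a frequency for such changes in this trial nor any record of such re-dosing. This reads as a drafting inconsistency, with nothing to suggest a deliberate choice to escalate.

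**Conclusion.** The concern holds. As written, the ST and T-wave rows of Table 5 raise romidepsin by 25% for a patient at the MTD, double it for a patient already reduced to 5 mg/m², and leave it unchanged at levels 3 and 4. They contradict Table 3, the rest of Table 5 and the declared MTD.

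The dose comparison rests on no assumption beyond the protocol's own tables. The effect on patients and on the phase IIa toxicity profile assumes that the row is followed literally at least once. The number affected among the 20 planned phase IIa patients cannot be estimated from the documents. Because the instruction concerns cardiac safety and points in the wrong direction, it must be fixed however rarely it would apply.

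**What to change.** Replace the fixed dose in the T-wave and ST-segment rows with a reference to Table 3, as the other restart rows already have, and remove the two further mentions of 10 mg/m². The recurrence sentence then needs a new rule, for example a further Table 3 step or removal from study. The clinical leads should choose it. The check to apply is that no row called a reduction names a dose at or above the one being given.

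Review the dosing records for any patient restarted under this row, and report such cycles separately as exposure above the MTD.

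The cost is a few words in one table and a record check in a trial that expects 30 patients. If the amendment is classed as a safety change, Section 16.3.1 also stops new enrolment at participating sites until their IRBs approve it. No sample size, stopping boundary or analysis changes.

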# NOTE: Cardiac findings that require dose modification should be reported as AEs or SAEs as appropriate.

<sup>a Measured from isoelectric line to peak of T-wave.

<sup>b Measured from isoelectric line to ST segment.

Memorial Sloan Kettering Cancer Center IRB Number: 14-179 A(6)
Approval date: 12-Dec-2017

Administrative Update 1:06-Dec-2018

# 9.5.3 Other Non-Hematologic and Hematologic Toxicities

All previously established or new toxicities observed any time, with the exception of those mentioned above, are to be managed as summarized in Table 5:

- Dose interruption or study discontinuation is not required for lymphopenia of any grade.
- In general, if study drug has been held and the toxicity does not resolve, as defined above, then drug must be discontinued.
- Dose reductions should not be performed for alopecia or for non-infectious diarrhea, nausea, or vomiting that was not treated with aggressive anti-diarrheal or anti-emetic support.

#### 9.6 Treatment Adherence

Research personnel will review the dosing instructions with patients. Patients will be provided with a medication diary and asked to record the drug administration. Patients will be asked to bring any unused drug and empty drug containers to the research personnel at the beginning of each cycle. Site staff will count and record the number of used and unused drug at the beginning of each cycle and reconcile with the patient diary.

Any unused Revlimid® (lenalidomide) should be returned to the patient for disposition in accordance with the Revlimid REMS program.

# 9.7 Concomitant Therapy

### 9.7.1 Recommended Concomitant Therapy

Subjects will receive full supportive care, including transfusions of blood and blood products, antibiotics, analgesics, and antiemetics when appropriate. Subjects should take prophylaxis against varicella zoster as per their institutional guidelines while on this regimen (e.g. acyclovir 400mg by mouth twice daily).

# 9.7.2 Anticoagulation Consideration

Lenalidomide increases the risk of thrombotic events in patients who are at high risk or with a history a thrombosis, in particular when combined with other drugs known to cause thrombosis. When lenalidomide was combined with other agents such as steroids (e.g. dexamethasone, prednisone), anthracyclines (Doxil, Adriamycin) and erythropoietin the risk of thrombosis is increased. For information on the risk of venous thromboembolism with combined oral contraception see Appendix A: Risks of Fetal Exposure, Pregnancy Testing Guidelines and Acceptable Birth Control Methods.

Consideration should be given to the optional use of aspirin (81 or 325 mg) or some other form of prophylaxis as deemed appropriate. Low molecular weight heparin may be utilized in patients that are intolerant to ASA. Coumadin should be

used with caution and close monitoring of INR. Carefully monitor prothrombin time (PT) and International Normalized Ratio (INR) in patients concurrently administered ISTODAX® and Coumadin derivatives.

If prophylactic anti-coagulation is used, it will be held for platelet counts < 50,000, and then restarted when platelet counts are above this level.

#### 10.1 EVALUATION DURING TREATMENT/INTERVENTION

# 10.2 Assessments During Treatment: Phase 1, cycle 1 and cycle 2; phase 2, cycle 1

A patient may receive treatment on day 1 or day 8 of the first cycle if he or she meets the following parameters on the day of treatment:

- ANC is ≥ 1.0 K/µL Platelet count is ≥ 80 K/µL or within 10 K/µL of baseline for cycle 1 day 1 and platelet count ≥ 50 K/µL for cycle 1 day 8. (In the Phase II portion, if thrombocytopenia is due to bone marrow involvement platelet count must be ≥ 50 K/µL),
- Serum creatinine concentration ≤ 2.0 × ULN or ≤ baseline Serum potassium must be confirmed to be greater than or equal to the lower limit of normal for the testing laboratory, or corrected to those levels.
  - Supplements must be given to patients whose potassi um and/or magnesium are below the aforementioned range.
    - Magnesium supplementation: If levels are below normal range, but within 0.5 units of the lower limit of normal, patients can receive at least 2gm magnesium IV and proceed to treatment without re-checking labs. Patients can be treated if magnesium levels are above normal range.
- Potassium supplementation: If levels are below normal range, but within 0.3 units of the lower limit of normal, patients can receive at least 20mEq potassium and proceed to treatment without re-checking labs. Any drug-related rash or neuropathy that may have occurred has resolved to ≤ grade 1 severity
- Any other drug-related adverse events that may have occurred have resolved to ≤ grade 2 severity.

#### Within 7 days of treatment:

- AST (SGOT) and ALT (SGPT) ≤ 3.0 × ULN.
  - Liver function analysis should be assessed on the day of treatment but does not have to be resulted prior to initiating treatment if the most recent assessment meets the above criteria and was performed within the last 7 days.

If these conditions are not met on Day 1 of a new cycle, the subject will be evaluated at least weekly and a new cycle of treatment will not be initiated until the toxicity has resolved as described above.

# 10.2.1 Assessments During Treatment: Phase 1, cycle 3 and beyond; phase 2, cycle 2 and beyond

A patient may initiate a new cycle if he or she meets the following parameters on the day of treatment:

- o ANC is ≥ 1.0 K/ $\mu$ L
- Platelet count is  $\ge 80$  K/ $\mu$ L or within 10 K/ $\mu$ L of baseline. (In the Phase II portion, if thrombocytopenia is due to bone marrow involvement platelet count must be  $\ge 50$  K/ $\mu$ L)

The following parameters may be checked within 3 days of initiating a cycle:

- o Serum creatinine concentration ≤ 2.0 × ULN or ≤ baseline
- Serum potassium and magnesium is ≥ the lower limit of normal for the testing laboratory, or corrected to those levels for the testing laboratory.
- If levels are within range romidepsin may be administered without repeat testing on day of treatment unless clinically indicated (such as vomiting, diarrhea, or initiation of medications that may affect electrolytes).
- Supplements must be given to patients whose potassi um and/or magnesium are below the aforementioned range:
  - Magnesium supplementation: If levels are below normal range, but within 0.5 units of the lower limit of normal, patients can receive at least 2gm magnesium IV and proceed to treatment without re-checking labs.

Potassium supplementation: If levels are below normal range, but within 0.3 units of the lower limit of normal, patients can receive at least 20mEq potassium and proceed with treatment without re-checking labs.

- Any drug-related rash or neuropathy that may have occurred has resolved to ≤ grade 1 severity
- Any other drug-related adverse events that may have occurred have resolved to ≤ grade 2 severity.
- ECG schedule as specified in Table 7.

## Within 14 days of treatment:

- AST (SGOT) and ALT (SGPT) ≤ 3.0 × ULN.
  - Liver function analysis should be assessed on the day of treatment but does not have to be resulted prior to initiating treatment if the most

Memorial Sloan Kettering Cancer Center IRB Number: 14-179 A(6) Approval date: 12-Dec-2017

Administrative Update 1: 06-Dec-2018

recent assessment meets the above criteria and was performed within the last 14 days.

If these conditions are not met on Day 1 of a new cycle, the subject will be evaluated at least weekly and a new cycle of treatment will not be initiated until the toxicity has resolved as described above.

# 10.3 Required Blood Parameters and Other Investigations Prior to Romidepsin Day 8

The following criteria must be fulfilled:

- ANC is ≥1.0 K/µL.
- Platelet count is ≥ 50 K/µL.
  - Serum potassium and magnesium is ≥ the lower limit of normal for the testing laboratory, or corrected to those levels for the testing laboratory.
  - o If levels are within range romidepsin may be administered without repeat testing on day of treatment unless clinically indicated (such as vomiting, diarrhea, or initiation of medications that may affect electrolytes).
  - Supplements must be given to patients whose potassi um and/or magnesium are below the aforementioned range.
    - Magnesium supplementation: If levels are below normal range, but within 0.5 units of the lower limit of normal, patients can receive at least 2gm magnesium IV and proceed to treatment without re-checking labs.
    - Potassium supplementation: If levels are below normal range, but within 0.3 units of the lower limit of normal, patients can receive at least 20 mEq potassium and proceed with treatment without rechecking labs.
- Recovery of any drug-related non-hematological toxicity to Grade 2 or less, unless otherwise indicated.
- ECG schedule as specified in Table 7.
- If any of these criteria are not fulfilled, then administration of study drugs should be delayed as detailed in Section 9.0.

## Within 7 days of treatment:

- AST (SGOT) and ALT (SGPT) ≤ 3.0 × ULN.
  - o Liver function analysis should be assessed on the day of treatment but does not have to be resulted prior to initiating treatment if the most recent assessment meets the above criteria and was performed within the last 7 days.

